### **9.2.3 Visit 2 - Baseline**

The time between visit 1 (screening), and visit 2 (baseline), will be no less than 24 hours and no more than 28 days (or up to 90 days with sponsor approval). In this visit a medication kit will be dispensed to him/her together with a leaflet of instructions for use. The subject will be given an emergency contact card with 24-hour contact numbers. The subject will be instructed to keep the contact card with him/her at all times.

The following activities will be performed:

- Dispensation of study medication kit
- Vital signs (HR, BP RR and temperature), weight and ECG
- Urine pregnancy test for women of childbearing potential
- Concomitant medications
- Adverse events review
- Inclusion/Exclusion criteria review
- Study drug dispensing and dosing instructions

- UPDRS II and III questionnaire
- CSSRS- SLV questionnaire
- CGI-S questionnaire
- PDQ39 questionnaire
- ESS questionnaire
- QUIP-RS questionnaire
- HRQOL SF-12v2
- Orthostatic hypotension scale question 1 for subjects with OH

The treatment should be started according to the dosing instructions the day after the baseline visit.

### **9.2.4 Visit 3**

At the end of week 3  $\pm 2$  days subjects will be required to visit the clinic for titration evaluation regarding their satisfaction and tolerability with the 1.5 mg dose of Pramipexole ER (or placebo). The dose may remain 1.5 mg or be increased to 3.0 mg. Additionally, the subject will continue to take 1 capsule a day of P2B001/PPX 0.6/RAS 0.75/placebo. The following activities will be performed:

- On-site evaluation of Pramipexole ER (or placebo) dose.
- Concomitant medications
- Adverse events review
- CSSRS-SLV questionnaire
- QUIP-RS questionnaire

### **9.2.5 Week 4 Phone Call**

At the end of week 4 a phone call to the subject will be conducted by the PI or sub-Investigator regarding the subject's satisfaction and tolerability of the treatment and the possible need for increase of the dose. During this phone call a review of adverse events and concomitant medications will also be done. In addition, if the PI or sub-Investigator deem necessary, an unscheduled visit for a titration evaluation may be conducted at this time.

### **9.2.6 Visit 4**

Visit 4 will take place 5 weeks after the baseline visit  $\pm 2$  days. The following activities will be performed:

- Evaluation of the pramipexole ER/placebo dose which may be changed if necessary only until the end of the next week, week 6.
- Vital signs (HR, BP RR and temperature) and weight
- Concomitant medications
- Adverse events review

- Study drug accountability
- Collection of the titration kit, (Weeks 1-4)
- UPDRS II, III
- CSSRS-SLV questionnaire
- QUIP-RS questionnaire
- ESS questionnaire
- CGI-I questionnaire
- Orthostatic hypotension scale question 1 for subjects with OH
- Laboratory tests for hepatic or renal function for subjects with mild hepatic failure or mild kidney failure respectively.

### **9.2.7 Visit 5**

Visit 5 will take place 8 weeks after the baseline visit and start of medication treatment  $\pm 2$  days. The following activities will be performed:

- Vital signs (HR, BP RR and temperature) and weight
- Concomitant medications
- Adverse events review
- Study drug accountability
- Collection of the maintenance kit (Box 1 of 2, weeks 5-8)
- UPDRS II, III
- CSSRS-SLV questionnaire
- QUIP-RS questionnaire
- ESS questionnaire
- CGI-I questionnaire
- Orthostatic hypotension scale question 1 for subjects with OH
- Laboratory tests for hepatic or renal function for subjects with mild hepatic failure or mild kidney failure respectively.

### **9.2.8 Visit 6 – Treatment Termination**

Visit 6 will be performed at the end of the treatment phase, 12 weeks  $\pm 2$  days after the baseline visit. The following activities will be performed:

- Vital signs (HR, BP RR and temperature), weight
- Concomitant medications
- Adverse events review
- Study drugs accountability
- Collection of maintenance kit (Box 2 of 2 Weeks 9-12)
- UPDRS II and III questionnaire
- CSSRS-SLV questionnaire

- CGI-S questionnaire
- CGI-I questionnaire
- PDQ39 questionnaire
- ESS questionnaire
- QUIP-RS questionnaire
- HRQOL SF-12v2
- Orthostatic hypotension scale question 1 for subjects with OH

### **9.2.9 Visit 7 – Safety Follow Up**

A follow up safety visit will be performed 2 weeks  $\pm$ 2 days after the termination visit. Safety parameters will be evaluated, as follows:

- Symptom-directed physical and neurological examination
- Vital signs (HR, BP RR and temperature), weight and ECG
- Concomitant medications
- Adverse events review
- Study drugs accountability
- Collection of down titration kit (week 13)
- Laboratory tests, including hematology, chemistry , urinalysis and a serum pregnancy test for women of childbearing potential (see Appendix II)
- CSSRS-SLV questionnaire
- QUIP-RS questionnaire

### **9.2.10 Unscheduled Visits**

If needed, an unscheduled visit may take place.

#### Unscheduled visit for titration follow-up

During the titration phase an unscheduled visit may be conducted to assess the need to raise or lower the dose of pramipexole ER/or placebo. In addition to the dose evaluation, a review of adverse events and concomitant medications will be conducted. No other study activities will be performed at this visit unless safety considerations arise (see next section).

#### Unscheduled visit for other reasons

An unscheduled visit may take place at any time during the study (e.g. PD symptoms or an AE that warrant personal evaluation). The following activities will be performed:

- Vital signs (HR, BP RR and temperature) and weight
- Concomitant medication
- Adverse events review
- Symptom-directed physical and neurological examination

- Completion of any uncompleted efficacy or safety scales, as needed

The date and reason for the visit and any data generated will be documented in the eCRF.

### **9.2.11 Early Treatment/Study Termination Visit**

Subjects who terminate treatment/study early (following first dose and prior to visit 6) according to criteria in section 7.5 will be requested to undergo a treatment/study termination visit. The treatment termination visit can be conducted as part of the next scheduled study visit if it is within 5 days of treatment termination. If the next scheduled visit is more than 5 days away it is preferable, if possible, to schedule an “unscheduled” visit as soon as possible. All efforts should be made to schedule the early treatment/study termination visit as close to the treatment/study termination as possible. **All activities listed in the treatment termination (visit 6) and safety visits (visit 7) will be performed at this visit.** The entire study medication kit with all boxes and bottles left should be returned. The date and reason for the ETT and any data generated from the ETT visit will be documented in the eCRF.

Subject will be requested to continue all study schedule activities as in section 9.2.11.1. If a subject refuses to take part in the scheduled study visits and activities it will be documented as early study termination and the Investigator shall only follow up on any safety issues if needed.

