**Duration of treatment:**

Subjects will receive study drug or matching placebo treatment for a total of 12 weeks followed by a 7-day gradual discontinuation of treatment of pramipexole ER arm or matching placebo).

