## 5.2 Dose Modification

Subjects may be allowed to miss a dose of study medication if:

- 1) Subject develops an adverse event that the Investigator believes requires the subject's dose to be held temporarily, or
- 2) Subject loses their kit of study medication and a replacement kit is requested, in this situation the PI should request an emergency shipment to alert the distributor to ship the replacement kit urgently).

During the pramipexole ER titration phase, the PI or sub-Investigator may modify (up or down) subject's dose to either 1.5, 3.0 or 4.5 mg of the pramipexole ER/identical placebo to reach the optimal tolerated therapeutic dose. Following the titration phase, after week 6, no modifications are allowed.

If the subject experiences intolerable adverse events, dosing may be held temporarily or withdrawn (all treatments, including both capsules and tablets, please note that pramipexole

ER/matching placebo tablets need to be down titrated gradually (see down titration instructions in section 6.1). However, the subject will continue to be followed-up according to the protocol pre-planned schedule of activities

No other dose modifications will be allowed in this study.

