Up-Titration phase: A 3-6 week double blind, double dummy titration phase with pramipexole ER or matching placebo. During this phase subjects will also take 1 capsule of P2B001/RAS 0.75/PPX0.6/Placebo which does not need titration. For the first 3 weeks the titration of the pramipexole ER will be increased by weekly increments up to a daily dose of 1.5 mg as follows: 0.375, 0.75 and 1.5 mg. If needed, between weeks 3 and 6, the titration can continue to a daily dose of 3.0 mg or 4.5 mg of pramipexole ER or matching placebo or reduced to a minimum of 1.5mg with the final level determined based on achieving satisfactory efficacy and tolerability. On completion of the dose-titration phase (end of week 6), the minimum therapeutic dose of Pramipexole ER 1.5 mg per day (or placebo) must be achieved by all the patients. The treatment with study medications of patients who cannot achieve this dosage will be discontinued, but the subject will be requested to continue with all the study visits.

Maintenance phase: Once the final dose level has been reached for the pramipexole ER, the subject will continue at that dose, together with the once daily P2B001/RAS 0.75/PPX0.6/Placebo capsule, until the end of Week 12.

Down-titration phase: a 7-day gradual down titration of pramipexole ER or matching placebo. The down titration should be done by reducing the dose every two days by half (except for subjects taking 4.5 mg, these should reduce the dose to 3.0 mg and then continue to reduce by half every two days). There is no treatment with once daily P2B001/RAS 0.75/PPX0.6/Placebo capsules during this period.

Safety follow-up phase: a 7 days period of no treatment of pramipexole ER and 14-day period of no treatment for the P2B001/RAS 0.75/PPX0.6/Placebo capsule.

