#### Early Treatment Termination (ETT)

A subject who discontinued study medication for any reason before the end of week 12 will continue pre-planned study schedule of activities as follow up. The subject will be requested to undergo a treatment termination visit as described in section 9.2.11

Please note that P2B001/PPX 0.6/RAS 0.75/Placebo capsules can be stopped immediately, while pramipexole ER/matching placebo tablets need to be gradually down titrated as described in section 6.1.

The reasons for withdrawal could include the following:

- Subject withdrawal of consent to be treated with study medication(s) but still consenting to participate in study visits and activities
- Request of the Investigator for any medical or other reason
- Request of the primary care physician via the Investigator
- Pregnancy
- Non-compliance
- Subject who cannot achieve the minimum therapeutic dose of pramipexole ER (or placebo) of 1.5 mg per day.
- Major protocol violation
- Adverse Event/Experience
- Lack of Efficacy
- Subjects who, according to the Investigator, need additional therapy that is excluded in the protocol for the treatment of the disease.
- Any other reason relating to the patient's safety or integrity of the study data.

If a subject suspect that she is pregnant, a urine test will be performed at the site. If the urine test is positive, study drug administration will be interrupted pending the results of a confirmatory blood/serum test. If the pregnancy is confirmed with a positive blood/serum test, then the subject will be permanently discontinued from study drug, but should participate in a Treatment Termination visit and continue with all the study visits as follow up visits up to and including safety follow up visit at week 14. The PI will follow the subject until she has given birth.

On completion of the dose-titration phase (end of week 6), the minimum therapeutic dose of pramipexole ER 1.5 mg per day (or placebo) must be achieved by all the patients. The treatment with study medications of patients who cannot achieve this dosage will be discontinued, but the subject will be requested to continue with all the study visits.

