### **9.2 Study Procedures**

#### **9.2.1 Detailed Study Plan**

A detailed Schedule of Activities is provided in Appendix I.

The study includes 7 visits. The first visit will allow screening of potential subjects that will participate in the study. This period of time between the screening visit and enrollment of a subject to the study is named the screening phase. The treatment phase is when subjects are receiving treatment with the study drugs. During the treatment phase, subjects' condition will be evaluated every 3-5 weeks (visits 2-6). The first 6 weeks of the treatment period will include a titration of the Pramipexole ER dose or its placebo to optimal dose (titration phase). One capsule a day of P2B001/PPX 0.6/RAS 0.75/Placebo will be taken at this time without any need for titration. This will be followed by a maintenance phase ending at the end of week 12. The safety follow up phase will start after week 12 which will include a week (week 13) of no treatment of the P2B001 or its components and a down-titration of pramipexole ER or its placebo. Week 14 will include no treatment at all. The end of the study drug treatment and a follow up safety visit will be performed at the end of week 14 (visit 7).

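### Subjects who stop early must taper the tablets, yet section 9.2.11 takes back the whole kit, taper box included, at a visit meant to come before the taper can finish

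*Protocol*

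**What the plan says.** Section 7.5 lets the capsules stop at once but says "pramipexole ER/matching placebo tablets need to be gradually down titrated as described in section 6.1". Section 5.2 repeats this where dosing is withdrawn for intolerable adverse events. Section 6.1 sets a nominal 7-day taper, halving every two days; for subjects on 4.5 mg, "these should reduce the dose to 3.0 mg and then continue to reduce by half every two days".

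For a subject who completes the study, termination comes before the taper. Section 9.2.8 is titled Treatment Termination and states that "Visit 6 will be performed at the end of the treatment phase". The synopsis describes treatment "for a total of 12 weeks followed by a 7-day gradual discontinuation of treatment of pramipexole ER arm or matching placebo", and section 9.2.1 places after week 12 "a week (week 13) of no treatment of the P2B001 or its components and a down-titration of pramipexole ER or its placebo".

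For a subject who stops early, section 9.2.11 says:

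- "The treatment termination visit can be conducted as part of the next scheduled study visit if it is within 5 days of treatment termination". Otherwise an unscheduled visit as soon as possible is preferred, and in every case the visit should be as near to the stop as can be managed. Section 10.3 also asks for a prompt visit.
- All visit 6 and visit 7 activities are done at this one visit. Visit 7 (section 9.2.9) includes collecting the week 13 down-titration kit.
- "The entire study medication kit with all boxes and bottles left should be returned".

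Section 12.7 has the whole kit counted at that visit. Section 9.2.11.1 then runs the follow-up visits with no study medication and no accountability, on the ground that the drug has already been handed in.

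**The concern.** The early termination visit merges a visit that normally precedes the taper (visit 6) with one that normally follows it (visit 7), and no step is left for the taper itself. A site that obeys section 9.2.11 promptly collects tablets that sections 5.2 and 7.5 say the subject must still take.

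What is at stake is subject safety and drug logistics. An abrupt stop of the tablets is what the protocol sets out to avoid. The risk falls on the pramipexole ER arm, mainly at 3.0 and 4.5 mg, because the other three arms taper placebo. Sites are blinded and cannot tell which subjects those are, so the rule has to be right for every arm.

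**Working it through.** The plan gives no figure to reproduce. The check is a timeline plus a reading of the supply rules.

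**Inputs.** Taper rule: section 6.1. Visit timing and return rule: section 9.2.11. Box contents: section 12.3. Planned arm size: section 15.

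**Convention.** Day 0 is the last capsule and the last full tablet dose. Day 1 is the first reduced dose, each step lasts two days, and the dose for the day of the visit is taken.

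**Taper schedule**

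| Starting dose | Steps | Length |
|---|---|---|
| 4.5 mg | 3.0 (days 1-2), 1.5 (3-4), 0.75 (5-6), 0.375 (7-8) | 4 × 2 = 8 days, or 7 if cut at the nominal week |
| 3.0 mg | 1.5 (1-2), 0.75 (3-4), 0.375 (5-6) | 3 × 2 = 6 days |
| 1.5 mg | 0.75 (1-2), 0.375 (3-4) | 2 × 2 = 4 days |

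**Daily dose being taken when the kit is returned**

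| Starting dose | Day 0 | Day 2 | Day 4 | Day 5 |
|---|---|---|---|---|
| 4.5 mg | 4.5 mg | 3.0 mg | 1.5 mg | 0.75 mg |
| 3.0 mg | 3.0 mg | 1.5 mg | 0.75 mg | 0.375 mg |
| 1.5 mg | 1.5 mg | 0.75 mg | complete | complete |

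**Taper days left after the visit** (length minus visit day; nominal 7-day version in brackets)

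- Day 2: 8 − 2 = 6 (7 − 2 = 5) from 4.5 mg; 6 − 2 = 4 from 3.0 mg; 4 − 2 = 2 from 1.5 mg.
- Day 5: 8 − 5 = 3 (7 − 5 = 2) from 4.5 mg; 6 − 5 = 1 from 3.0 mg; 0 from 1.5 mg.

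So from 3.0 or 4.5 mg every visit on days 0 to 5 falls before the taper ends. From 1.5 mg, visits on days 0 to 3 do.

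**How much of that matters.** Section 7.5 accepts an immediate stop of a capsule holding 0.6 mg of pramipexole. I therefore treat an abrupt stop from 0.75 mg or less as minor; this is my assumption. The dose exceeds 0.75 mg on days 0 to 4 from 4.5 mg, days 0 to 2 from 3.0 mg, and day 0 only from 1.5 mg. Doses above 1.5 mg begin only after the end of week 3, so earlier stops carry little risk.

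**Could other planned supply cover the taper?** Steps below 1.5 mg need 0.375 mg tablets, since the labels forbid cutting. The weeks 5-12 boxes hold 1.5 mg tablets only, and the weeks 1-4 box goes back at visit 4. After visit 4 the week 13 box is the only planned source of 0.375 mg tablets, and section 12.3 foresees no later dispensing.

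**Tablets to leave with the subject.** The most needed is for the 8-day taper from 4.5 mg. At 1.5 mg strength: 2 days × 2 + 2 days × 1 = 6. At 0.375 mg strength: 2 days × 2 + 2 days × 1 = 6.

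**Exposure ceiling.** 75 / 525 = 14.3% of planned subjects are on active tablets.

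**The case against.** The best defence is that termination of treatment could mean the last taper tablet. The protocol's usage is not uniform. Section 9.2.1 loosely puts the end of study drug treatment at visit 7. Section 6.1 counts 7 untreated days for the tablets but 14 for the capsule, so taper days count as tablet treatment. Section 5.2 mentions the taper in the same sentence as withdrawal of both products. If termination means the last tablet, returning the whole kit at the visit is coherent.

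The protocol does not say this for early stoppers, and it fits poorly. Visit 6 carries the name Treatment Termination and precedes the taper. Section 9.2.1 puts the taper in the safety follow-up phase. Its remark about week 14 cannot be literal, because week 14 has no treatment at all. What stands is that the term needs a definition.

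Second, the return and timing instructions are softly worded and set no fixed deadline, so an investigator can wait for the taper to finish. That is true, and then nothing is lost, but it goes against the request for a prompt visit in sections 9.2.11 and 10.3.

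Third, section 12.2 allows a replacement kit when a subject runs out for any reason. Section 12.6 expects it at the site in 1-2 days, or 3-4 over a weekend, and it would replace tablets just collected.

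Fourth, the dosing instruction leaflet is not among the documents and may cover the point. That stands as a caveat, though a leaflet should not have to override protocol text.

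**Conclusion.** The concern holds. The stated rules, followed as written, take back tablets that the protocol says the subject needs. This is a contradiction between instructions and not merely a missing detail, and it should be corrected.

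The size is limited. The worst case is an abrupt stop from 4.5 mg a day. Under the 0.75 mg assumption, the material window is up to 4 days after the last full dose from 4.5 mg, up to 2 days from 3.0 mg, and the day itself from 1.5 mg. The ceiling is the 75 planned pramipexole ER subjects. The true number would be some part of those who stop early, and it cannot be estimated because the documents give neither an early-stop rate nor a dose distribution. The SAP addendum shows that the route was used: 13 subjects across the blinded arms stopped before week 5 and were assessed at an unscheduled termination visit. It does not show that any of them lost taper tablets.

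The conclusion rests on reading early treatment termination as the last capsule and last full tablet dose. It makes no claim about power, type I error or the primary analysis.

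**What to change.** Amend three sections.

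- **9.2.11:** exempt the week 13 box from return at the early termination visit, or leave enough tablets to finish the taper (at most 6 × 1.5 mg and 6 × 0.375 mg). State that treatment termination for these subjects is the last capsule, matching the convention for completers.
- **9.2.11.1:** make the taper tablets an exception to the rule of no study medication during follow-up, and add one accountability step.
- **12.7:** count the taper box at the next scheduled visit or contact instead of at the termination visit.

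Apply this to all arms to keep the blind. Telling sites to wait until the taper ends would also remove the conflict, but it would put the visit 4 to 8 days after the last capsule and give up the prompt assessment the protocol asks for.

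The cost is a few sentences and one later count per early stopper. A subject who then refuses further visits may not bring the box back. Randomization, sample size and analysis are unchanged.

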#### ***9.2.11.1 Follow-up visits of subjects that have terminated the study treatment early***

ETT subjects will be requested to continue with all study visits and activities as planned, for follow up, without taking any study medication. During these visits, all questionnaires and assessments will continue as planned for follow up. Accountability will be omitted since study drug was returned at the ETT visit.

Subjects may take rescue therapy during the follow-up visits; this will be documented in the concomitant medication list.

ETT subjects that decided later to stop their participation in the study will be requested to undergo a study termination visit. **All activities listed in the treatment termination (visit 6) and safety visits (visit 7) will be performed at this visit.**

## **10 CONCOMITANT MEDICATIONS**

All concomitant medication that the subject is taking from the screening visit should be recorded on the concomitant medications log. In addition, any changes in concomitant medication or new medications added, including as a result of an inter-current illness must be recorded in the case report forms. A separate log will record anti-PD medications taken prior to enrollment.

### **10.1 Prohibited Medication**

Subjects must not receive concomitant therapy with any of the following:

- Other investigational therapy (washout period 30 days prior to study entry, baseline visit)
- Previous MAO-B inhibitors, selegiline or rasagiline, for longer than 4 weeks or within the previous 3 months prior to baseline visit.
- Previous levodopa or dopamine agonists, for longer than 4 weeks or within the previous 2 months prior to baseline visit.
- Previous anticholinergic drugs for PD (such as benztropine, orphenadrine hydrochloride, biperiden, ethopropazine, procyclidine, trihexyphenidyl) or amantadine for longer than 4 weeks; if previous exposure was less than 4 weeks then it must not be within 1 month prior to the baseline visit.
- Subjects can take peripheral anticholinergic drugs (such as oxybutynin, orphenadrine citrate, tiotropium bromide etc..) if they are stable on low dose for at least 4 weeks prior to study entry, and without (or with minor) cognitive effects; however, once enrolled into the study use of new peripheral anticholinergic drugs is prohibited. Patients should be followed very closely for possible cognitive side effects.
- Non selective MAO inhibitors, such as phenelzine or tranylecypromine
- Dopamine antagonists, such as the neuroleptics (phenothiazines, butyrophenones, thioxanthenes) or metoclopramide.
- Ciprofloxacin or other CYP1A2 inhibitors: may affect rasagiline plasma concentrations.
- Antitussive agent Dextromethorphan.: co-administration with rasagiline may lead to psychosis.
- Analgesic agents such as tramadol, methadone, meperidine and propoxyphene due to risk of serotonin syndrome.
- St. John's Wort or cyclobenzaprine (tricyclic muscle relaxant).
- Marijuana or previous exposure to Marijuana during the last 30 days prior to the baseline visit.

Care should be taken to avoid or minimize use of sympathomimetic medications, including nasal, oral and ophthalmic decongestants and cold remedies due to possible hypertensive reactions.

Care should be taken when giving study drugs with sedating medications (e.g. Diphenhydramine, Doxylamine Succinate and other first generation antihistamines) due to possible additive sedative effects with pramipexole.

Special attention should be given to symptoms and signs of serotonin syndrome, when an antidepressant is administered concomitantly with the study medication. Subjects who are taking

tricyclic or tetracyclic antidepressants, SSRIs, SNRIs or triazolopyridine antidepressants will be closely followed up by the PI for signs of serotonin syndrome, including: agitation or restlessness, confusion, rapid heart rate and high blood pressure, dilated pupils, loss of muscle coordination or twitching muscles, muscle rigidity, heavy sweating, diarrhea, headache, shivering or goose bumps. At each periodic meeting, the DSMB will review adverse events and vital signs reported for subjects taking antidepressants concomitantly. Severe or serious adverse events for such subjects will be reported to the DSMB within 48 hours of receipt of the report by the sponsor.

